24.10 Subgroup analysis

Heterogeneity of the primary outcome, split by centre, will be explored using a forest plot.

24.11 Interim analyses

The main outcomes will be analysed as stated in the analysis plan and will not be analysed as an interim analysis.

24.12 Stopping Rules

No formal interim analyses with stopping guidelines are planned. An independent Data Safety and Monitoring Committee (DSMC) will review the accumulating data at regular intervals and may recommend pausing or stopping the trial in the event of safety concerns.

24.13 Level of Statistical Significance

All principal analyses will be performed at the 2-sided 5% significance level.

24.14 Procedure for accounting for missing, unused and spurious data

The procedure for handling spurious or missing data will be described in the SAP. The trial will attempt to collect data as completely as possible.

The main analysis will include participants for whom endpoint data are available, with other participants being censored after their last available relevant outcome measure. It is anticipated that there will be minimal participant attrition. The sample size calculation has been adjusted to account for loss to follow-up or patient death.

24.15 Procedures for reporting any deviation(s) from the original statistical analysis plan Any deviation(s) from the original SAP will be described in the final report.

24.16 Health economics analysis

There are no health economic analyses to be undertaken as part of the trial.

24.17 Internal pilot/Decision Points

An internal pilot phase to assess the feasibility of recruitment will be conducted. This timepoint was chosen to ensure that five centres are open to recruitment and 20 participants are randomised. Recruitment is expected to last for 36 months, however there will be a formal review after an internal pilot phase of 9 months of recruitment. Stop-go criteria for this pilot phase are given in table 6 together with the progression guidance.

SENTINEL_Protocol_V1.1_27Apr2023.docx IRAS number: 318347 REC Reference: 23/LO/0248

Table 6: Stop-go criteria for internal pilot phase

Progression guidance	Participants randomised
Continue with study – no action required	>20 participants
Continue with study – action required:	13-20 participants
Review recruitment strategies	
Report to TSC	
Stop	<13 participants

The Trial Management Group (TMG) will closely monitor the progression criteria during the internal pilot, and together with the Trial Steering Committee (TSC) and Data and Safety Monitoring Committee (DSMC) will perform a full review towards the end of the internal pilot. The TSC and funder will make the final decision to terminate the study.

The internal pilot will mirror the procedures and logistics undertaken in the main definitive study. Data from the internal pilot will contribute to the final analysis.

Should a decision be made to stop the study, all randomised participants will be followed up per protocol. It is intended that the study will progress seamlessly from the internal pilot phase to the main recruitment phase.

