10.8 Expected recruitment rate

During the 2019-2020 financial year, a total of 156 lung transplants were carried out across all centres in the UK. We estimate that approximately 75% of patients would meet the eligibility criteria for the trial, and that approximately 30-40% of eligible patients will consent to take part in the trial (which we consider is a conservative but realistic estimate). Therefore, once all sites are open, we expect recruitment of 4-5 patients per month (approximately 1 patient per month/per centre). We anticipate one centre per month, following the study opening to recruitment, with all 5 centres open by month 12 at the latest. Therefore, assuming staggered opening of sites, randomisation of 152 participants should be feasible within the 36-month recruitment period.

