24.2 Sample Size/Power calculations

The anticipated 12-month rejection rates for lungs in the control arm by 12 months is 80%. Published rates vary between 33-100% (43–46) depending on definition and grade of rejection and method of analysis. However, a comprehensive study of regular transbronchial biopsies in 299 lung transplant patients showed a cumulative incidence of rejection (≥grade A1) of 91.7% in the first 12 months and (≥grade A2) of 77.9% (46).

In the SSF intestinal study, we observed a 72% reduction in biopsy-proven acute rejections from the 77% rejection rate in the control arm reducing to 22% in the with skin arm. However, as a more conservative estimate for this study, we consider a relative reduction of a third from 80% to 53.33% (corresponding to an absolute difference of 26.67%) to be clinically meaningful. 128 participants who have had a transplant are required for the analysis to achieve 90% power at a two-sided significance level of 5%. To allow for a 15% loss to follow-up or death by 12 months (76 per trial arm) 152 participants need to have been randomised and transplanted. In total, approximately 254 randomisations will be required to achieve this number and account for participants not proceeding with transplant.

Assessment of the diagnostic accuracy of the SSF compared to the current reference standard (organ biopsy) is a secondary objective of this study, and is undertaken in participants who received an SSF. Assuming approximately 80% specificity, and 90% specificity, based on previous studies, 95% confidence intervals (Wilson method) around the sensitivity, specificity, positive and negative predicted values will have a width of approximately 20-30%, depending on the observed sensitivity, specificity and event rates. A sample size of 64 participants receiving SSF and providing one-year follow-up data, an expected rejection rate of 53%, and anticipated values of 80% and 90% for sensitivity and specificity, respectively, will provide approximately 80% power (at a one-sided 5% significance level) to show that the observed sensitivity and specificity in the study are statistically significantly higher than 60% and 70%, respectively.

Since the proposed mechanistic sub-studies are intended to be hypothesis generating, no formal sample size calculations have been performed.

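### The internal pilot's no-action line (21 randomised at month 9) is not tied to the 254 randomisations and 152 transplanted participants the design needs, and sits below the on-course number for them

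*Protocol*

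**What the plan says.** Protocol 24.17 plans that "there will be a formal review after an internal pilot phase of 9 months of recruitment", out of 36 months of recruitment, and explains the timing: "This timepoint was chosen to ensure that five centres are open to recruitment and 20 participants are randomised". Table 6 has one criterion, the number of participants randomised. More than 20 means continue without action (green), 13 to 20 means continue with a recruitment review and a report to the steering committee (amber), and fewer than 13 means stop.

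Protocol 24.2 sets the target in a different unit. It needs 128 transplanted participants for analysis. It adds an allowance ("To allow for a 15% loss to follow-up or death by 12 months") to reach 152 randomised and transplanted, and then states that "approximately 254 randomisations will be required to achieve this number". Section 24.9 restricts the main analysis to participants who were randomised and transplanted. Sections 15.5 and 16.3 return participants who are not transplanted to the waiting list and allow them to be randomised again.

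Protocol 10.8 expects one centre to open per month, "with all 5 centres open by month 12 at the latest", and 4 to 5 recruits per month once all are open (about one per centre per month). It judges 152 randomisations feasible in 36 months and does not mention 254.

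**The concern.** Table 6 is the only prespecified recruitment criterion in the protocol. Its unit is not the unit of the sample size. Roughly 40% of randomisations are expected not to end in a transplant (1 − 152/254), and a count of participants randomised does not show that loss. Nor does the table say whether a participant who is randomised twice counts once or twice.

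The green line also appears low. If it is below the number a trial on course for 254 would have at month 9, the review can return no action for a trial heading for materially less than the stated 90% power. Corrective steps would then start later than they could have.

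**Working it through.** **Reproducing the plan's figures.** Inputs from 24.2: control 80%, intervention 53.33%, two-sided 5%, power 90%, loss 15%. With mean proportion 0.6667:

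- n per arm = [1.96·√(2·0.6667·0.3333) + 1.2816·√(0.8·0.2 + 0.5333·0.4667)]² / 0.2667² = (1.3067 + 0.8194)² / 0.0711 = 63.6, so 64 per arm and 128 in total.
- 64/0.85 = 75.3, so 76 per arm and 152 in total.
- 152/0.6 = 253.3, which agrees with about 254. The implied yield is 152/254 = 0.598 transplants per randomisation.

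**Projection from month 9.** Assumptions: a constant rate per open centre, randomisations starting on the day a centre opens, and the 0.598 yield. Let S be the centre-months open by month 9 divided by those open by month 36.

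- On course at month 9: 254·S randomisations, or 152·S transplanted.
- Lowest green result: 21/S randomisations by month 36, times 0.598 transplanted, times 0.85 analysable.
- Power = Φ{[0.2667·√n − 1.3067]/0.6394}, where n is analysable participants per arm. At n = 64 this returns 90%, as planned.

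Example, centres opening at months 0 to 4: by month 9, 9+8+7+6+5 = 35 centre-months; by month 36, 36+35+34+33+32 = 170; S = 0.206. On course is 254·0.206 = 52.3 randomisations or 152·0.206 = 31.3 transplanted. A count of 21 gives 21/0.206 = 102 randomisations, 61 transplanted, 52 analysable (25.9 per arm) and 53% power.

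| Centres open at months | Centre-months, month 9 / 36 | On course: randomised / transplanted | 21 projects to: randomised / transplanted | Power |
|---|---|---|---|---|
| 0, 1, 2, 3, 4 | 35 / 170 | 52 / 31 | 102 / 61 | 53% |
| 1, 2, 3, 4, 5 | 30 / 165 | 46 / 28 | 115.5 / 69 | 59% |
| evenly to 9 | 22.5 / 157.5 | 36 / 22 | 147 / 88 | 69% |
| evenly to 12 | 18 / 150 | 30 / 18 | 175 / 105 | 77% |

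**Against the protocol's own forecast.** Four to five per month over five centres is 0.8 to 1 per centre-month. With one centre opening per month from month 0, that gives 0.8·35 = 28 to 1·35 = 35 randomisations by month 9. The green line of 21 is below this.

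**10.8 against 24.2.** Over 36 months, 4 to 5 per month gives 144 to 180. Reaching 254 needs 254/36 = 7.1 per month. The forecast matches 152 randomisations, not 254.

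**The timing sentence.** 24.17 says month 9 ensures that five centres are open, whereas 10.8 allows the fifth to open as late as month 12. The same sentence aims for 20 randomised, but exactly 20 falls in the amber band.

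**The case against.** A reader might infer that a green result certifies a trial on course for about 61 transplanted, well under half of 152. The documents do not support that as a general statement.

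- **Schedule.** The figure of 61 belongs to one opening schedule. On the even opening to month 12 the result is 105, or 69% of 152. On that schedule 10.8's own rate gives only 14 to 18 randomisations by month 9 (0.8·18 to 1·18), so 21 would be above forecast there, though still below the 30 needed.
- **Start-up lag.** Randomisation needs Stage 1 consent on the waiting list, a donor offer that includes skin, and Stage 2 consent, so a new centre starts with no consented pool. With an assumed 3-month lag at each centre (openings at months 0 to 4), month 9 holds 20 of 155 centre-months. On course is then about 33, and 21 projects to about 97 transplanted (about 74% power). With 4 months it is 15 of 150, about 25 on course and about 126 transplanted (about 84%). With 5 months it is 10 of 145, so on course is 254·10/145 = 17.5 and 21 would suffice. That last case requires 21/10 = 2.1 randomisations per centre-month, about twice the rate in 10.8.
- **Units.** 254 counts randomisations; Table 6 counts participants, who may be randomised again. Per unique participant the eventual yield lies between 0.6 and 1. At a yield of 1, and with no lag, 21 projects to 102 transplanted on the fast schedule (about 76% power) and 175 on the slow one.
- **Oversight.** Table 6 is labelled as guidance. The management group meets about monthly, the steering and monitoring committees at least yearly, and the transplant outcome is recorded (17.3). The loss after randomisation is therefore visible to the people reviewing, even though the criterion does not count it.
- **Five centres.** Under the expected plan all five are open well before month 9. Only the outer bound in 10.8 conflicts, so this is a wording repair.

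These points make the size uncertain. They do not link the threshold of 21 to the 254 or the 152, and they do not settle what Table 6 counts.

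**Conclusion.** The concern holds as a should-fix. The pilot criterion is in a different unit from the sample size, and its no-action line of 21 is below the roughly 30 to 52 randomisations on course for 254 under the opening schedules 10.8 allows. At a constant rate per open centre, no start-up lag and the 152/254 yield, the lowest green result projects to about 61 transplanted (about 53% power) at one centre per month and about 105 (about 77%) with openings spread to month 12.

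Without a lag, 152 is reached only by slow opening combined with near-complete eventual transplantation (152/175 = 87% of participants). A lag moves every figure up, and a long one could close the gap; the protocol states none. That the line falls short of the design's needs is well supported under the protocol's stated inputs. The exact shortfall is not. No estimand, analysis or safety provision is affected.

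**What to change.** 1. In Table 6, report both randomisations and participants randomised and transplanted, and say whether a re-randomised participant counts once or each time.
2. State one opening schedule, with any start-up lag, and set the no-action line at the number on course for 254 and 152 under it. With no lag this is about 52 randomisations or 31 transplanted for one centre per month, and about 30 or 18 for openings spread to month 12.
3. Reconcile 10.8 (152 randomisations, 4 to 5 per month) with 24.2 (254, about 7 per month), and only then re-derive the amber and stop lines. Scaling the present 13/20 ratio to 31 would give a stop line near 20 transplanted (31·13/20 = 20.2), which should not be adopted. A trial recruiting exactly as 10.8 plans would have only about 17 to 21 transplanted at month 9 (28·0.598 to 35·0.598), and the on-course figure for slow opening is 18.
4. Align the five-centres sentence in 24.17 with the month-12 limit in 10.8, and place exactly 20 in the intended band if 20 is the target.

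The cost is an edit to one table and a few sentences in 24.17 and 10.8. The downside is a higher chance of an amber review.

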25 DATA MANAGEMENT

The data management aspects of the study are summarised here with details fully described in the Data Management Plan. See section on patient confidentiality for information on management of personal data.

25.1 Source Data

Source documents are where data are first recorded, and from which participants' CRF data are obtained. For this study, source data will include the following:

- Hospital medical records (from which data will be summarised into the CRF)
- Biopsy reports
- Patient-reported outcome measures that are submitted directly to the study office

25.2 Location of source data

The location of source data in the study is listed with the tables within the section OBJECTIVES AND OUTCOME MEASURES.

25.3 Case report forms (CRFs)

The Investigator and study site staff will ensure that data collected on each participant is recorded in the CRF as accurately and completely as possible. Details of all protocol evaluations and investigations must be recorded in the participant's medical record for extraction onto the CRF.

All appropriate laboratory data, summary reports and Investigator observations will be transcribed into the CRFs from the relevant source data held in the site medical record(s).

All documents will be stored safely in confidential conditions. On all study-specific documents, other than the signed consent, the participant will be referred to by the study participant number/code, not by name.

25.4 Non-CRF data

All trial data will be recorded on the CRF. No additional data will be held outside of the CRF.

Translational study data from analysis of samples will be kept on the secure server identifiable only by study ID, and accessible only by appropriate members of the research team.

25.5 Access to Data

To ensure compliance with regulations, direct access will be granted to authorised representatives from the Sponsor and host institution to permit trial-related monitoring, audits and inspections. The data submitted by study participants directly via the study database (i.e. electronic patient reported outcomes) will also be made available to the participating site.

25.6 Data Recording and Record Keeping

The case report forms will be designed by members of the trial management team which will include the Chief Investigator, study statisticians and study trial manager.

Data will, wherever possible, be collected in electronic format with direct entry onto the study database by site staff or participants. Electronic data collection has the major advantage of building "data logic" into forms, minimising missing data, data input errors and ensuring the completeness of consent and assent forms. REDCap (Research Electronic Data Capture) is a secure, web-based application designed to support data capture for research studies, providing 1) an intuitive interface for validated data entry; 2) audit trails for tracking data manipulation and export procedures; 3) automated export procedures for seamless data downloads to common statistical packages; and 4) procedures for importing data from external sources.

All data entered will be encrypted in transit between the client and server. All electronic patient-identifiable information, including electronic consent forms, will be held on a server located in an access-controlled server room at the University of Oxford. The data will be entered into a GCP compliant data collection system and stored in a database on the secure server, accessible only to members of the research team based on their role within the study. The database and server are backed up to a secure location on a regular basis. Details of the data collected, where it is stored and who has access to it along with a fair processing statement will be available for the public to see on the study website. Paper forms with patient identifiable information will be held in secure, locked filing cabinets within a restricted area. The identifiable data will be kept separately from the outcome data obtained from/about the patients (both paper and electronic). Patients will be identified by a study ID only.

Direct access to source data/documents will be required for study-related monitoring and/or audit by the Sponsor, NHS Trust or regulatory authorities as required.

Contact details will be retained until the website link publishing the results of the study can be sent out, or for longer where consent is in place for future research. The data management and sharing plan will list explicitly when sensitive personal information will be destroyed.

Data captured during phone calls to participants or from paper-based study questionnaires returned to the SENTINEL study office will be entered into the study database by suitably trained central office staff. Full details will be recorded in the Data Management Plan. The participants will be identified by a unique study specific number in any data extract. Identifiable data will only be accessible by members of the study team with a demonstrated need (managed via access controls within the application) and only used to communicate with the participant (e.g. for study sending follow-up reminders for online form completion or telephone follow-up).

26 QUALITY ASSURANCE PROCEDURES

A rigorous programme of quality control will be implemented. The study management group will be responsible for ensuring adherence to the study protocols at the study sites. Quality assurance (QA) checks will be undertaken by OCTRU to ensure integrity of randomisation, study entry procedures and data collection. The OCTRU has a QA team who will monitor this study by conducting audits (at least once in the lifetime of the study, more if deemed necessary) of the Trial Master File and compliance with requirements in OCTRU SOPs. The study will undergo a formal check of the documentation as part of OCTRU giving the Green Light to open the study. Furthermore, the processes of obtaining consent, randomisation, registration, provision of information and provision of treatment will be monitored by the trials unit staff. Written reports will be produced for any oversight committees as applicable, informing them if any corrective action is required. Additionally, the study may be monitored, or audited by sponsor or host sites in accordance with the current approved protocol, GCP, relevant regulations and standard operating procedures. A study-specific data management and monitoring plan will be in place prior to the start of the study.

26.1 Audit and regulatory inspection

All aspects of the trial conduct may be subject to internal or external quality assurance audit to ensure compliance with the protocol, GCP requirements and other applicable regulation or standards. It may also be subject to a regulatory inspection. Such audits or inspections may occur at any time during or after the completion of the study. Investigators and their host Institution(s) should understand that it is necessary to allow auditors/inspectors direct access to all relevant documents, study facilities and to allocate their time and the time of their staff to facilitate the audit or inspection visit. Anyone receiving notification of a Regulatory Inspection that will (or is likely to) involve this trial must inform the Trial Office without delay.

26.2 Risk Assessment

This protocol is designed to deliver a risk-adapted approach to conducting the research. A risk assessment has been conducted and a monitoring plan will be prepared before the trial opens. The known and potential risks and benefits to participants have been assessed in comparison to those of standard of care. A risk management strategy is in place and will be reviewed and updated as necessary throughout the trial or in response to outcomes from monitoring activities. Monitoring plans will be amended as appropriate.

26.3 Trial monitoring

Monitoring will be performed according to a study-specific monitoring plan. Data will be evaluated for compliance with the protocol, completeness and accuracy. The investigator

and institutions involved in the study will permit study-related monitoring and provide direct on-site access to all study records and facilities if required. They will provide adequate time and space for the completion of monitoring activities.

Study sites will be monitored centrally by checking incoming data for compliance with the protocol, consistency, completeness and timing. The case report data will be validated using appropriate set criteria, range and verification checks. The study site must resolve all data queries in a timely manner. All queries relating to key outcome and safety data and any requiring further clarification will be referred back to the study site for resolution.

Note: 'in a timely manner' means within no more than 7 working days of the data query and within 28 days of receipt of a data query unless otherwise specified.

The Trial Office will decide the maximum CRF lag time based on protocol requirements and feasibility. In general, a 2 week turn around is an acceptable default for all non-urgent data.

Study sites will also be monitored remotely and/or by site visit, as necessary, to ensure their proper conduct of the trial. Trial Office staff will be in regular contact with site personnel to check on progress and deal with any queries that they may have. Where on-site monitoring is conducted. monitoring reports will be sent to the site in a timely fashion. The Investigator is expected to action any points highlighted through monitoring and must ensure that corrective and preventative measures are put into place as necessary to achieve satisfactory compliance, within 28 days as a minimum, or sooner if the monitoring report requests.

